7.4.1.4. Stable Disease (SD)

Neither sufficient shrinkage to qualify for PR nor sufficient increase to qualify for PD, taking as reference the smallest sum LD since the treatment started.

7.5. Evaluation of Best Overall Response

The best overall response is the best response recorded from the start of the treatment until disease progression/recurrence (taking as reference for progressive disease the smallest measurements recorded since the treatment started). The patient's best response assignment will depend on the achievement of both measurement and confirmation criteria.

Table 6. Response Evaluation

Target Lesions	Non-Target Lesions	New Lesions	Overall Response	Best Response for this Category Also Requires:
CR	CR	No	CR	>4 wks confirmation
CR	Non-CR/Non-PD	No	PR	>4 wks confirmation
PR	Non-PD	No	PR	
SD	Non-PD	No	SD	Documented at least once >4 wks from baseline

PD	Any	Yes or No	PD	no prior SD, PR or CR
Any	PD*	Yes or No	PD	
Any	Any	Yes	PD	

* In exceptional circumstances, unequivocal progression in non-target lesions may be accepted as disease progression.

Note: Patients with a global deterioration of health status requiring discontinuation of treatment without objective evidence of disease progression at that time should be reported as "symptomatic deterioration". Every effort should be made to document the objective progression even after discontinuation of treatment.

Note: If patients respond to treatment and are able to have their disease resected, the patient's response will be assessed prior to the surgery.

7.6. Definition of Disease Progression

Disease progression will be defined as:

- Progression of disease by RECIST v1.1 criteria.
- Clinical progression as determined by the Investigator, which may be characterized as, but is not limited to:
 - Increase of at least 2 points in ECOG performance status attributable to cancer progression.
 - Requirement for palliative chemotherapy or surgery.
- Death from any cause that is not unequivocally unrelated to disease progression (e.g. motor vehicle accident)

8. STATISTICAL CONSIDERATIONS

8.1. Objectives

8.1.1. Primary Objective:

To determine the objective response rate (ORR) of SM-88 plus the conditioning agents methoxsalen, phenytoin, and sirolimus (MPS) in patients with advanced HR+/HER2 negative breast cancer.

8.1.2. Secondary Objectives:

To assess:

- Progression free survival (PFS),
- Clinical benefit rate (CBR) at ≥ 24 weeks,
- Duration of response (DOR), and
- Safety/tolerability (adverse events, serious adverse events, incidence of dose delays or dose reductions, treatment discontinuations due to adverse events, and all deaths).

8.1.3. Exploratory Objectives:

To evaluate cell-free DNA (cfDNA) at baseline (pre-treatment on C1D1), during treatment, and at disease progression.

8.2. Study Design

This is a multicenter phase II trial with single arm, open-label study of SM-88 used with MPS in metastatic HR+/HER2- breast cancer. The primary endpoint of this phase II study is to determine the ORR of SM-88 therapy in patients with metastatic HR+/HER2- breast cancer. The phase II portion of the trial will follow Simon's minimax two-stage design (Simon 1989).

In the Stage 1, 30 patients will be accrued. If there are 2 or fewer objective responses among these 30 patients with the SM-88 plus MPS therapy, the therapy will be rejected and the trial stopped. However, if 3 or more patients achieve an objective response in the Stage 1, then an additional 20 patients will be enrolled in Stage 2, for a total of 50 patients in this phase II study. If 8 or more patients exhibit an objective response among these 50 patients, then the treatment will be considered for further investigation. Any unplanned interim analysis, e.g., due to slow accrual, external information, etc, will utilize the sequential conditional probability ratio test (TAN and XIONG 1996, Tan and Xiong 2011), which allows an early assessment of statistical evidence for both efficacy and futility while retaining the rigor of the trial and provides a discordance probability that early trend could be reversed should the trial continue to enroll all 50 patients.

8.3. Sample Size Considerations

This proposed phase II study will utilize the Simon's minimax two-stage design (Simon 1989). The desirable ORR is 20% (based on the ORR of 19.7% seen with abemaciclib monotherapy in the MONARCH 1 Phase II clinical trial, which was conducted in \geq 3rd line treatment of metastatic HR+/HER2- breast cancer)(Dickler, Tolaney et al. 2017) and the undesirable ORR of 9.5% (based on ORR of 9.5% seen in a trial of exemestane plus everolimus in the Phase III BOLERO-2 study in patients who had progressed on a non-steroidal aromatase inhibitor and had a median of 3 previous therapies) (Baselga, Campone et al. 2012).

The null hypothesis is that the true response rate is 0.095, and the alternative hypothesis is that the true response rate is 0.2. The trial is carried out in two stages. In Stage 1, a total number of 30 patients is accrued. If there are 2 or fewer responses among these 30 patients, the study will be stopped early. Otherwise, additional 20 patients will be accrued in Stage 2, resulting in a total number sample size of 50. If there are 8 or more responses among these 50 patients, we reject the null hypothesis and claim that the treatment is promising. The design controls the type I error rate at 0.1 with a power of 0.8.

8.4. Endpoints and Analysis Plans

P-value less than 0.05 will be considered significant. All statistical analyses will be performed using RStudio (Version 0.99.902) and SAS (Version 9.4).

8.4.2.1. Duration of Response (DoR)

The distribution of duration of response (DOR) will be estimated by Kaplan-Meier methodology, and the median of the DOR with 95% CI will be reported (calculated based on Kaplan-Meier).

8.4.2.2. Progression Free Survival (PFS)

The PFS is defined as the time in days from study entry to the first documented disease progression per RECIST v1.1 as assessed by local site or death. Patients who are alive and free from progression on the date of closing follow-up will be censored on that date. PFS will be estimated by Kaplan-Meier methodology, and median PFS with 95% CI will be reported.

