4.3.12.1. Discontinuation of Individual Patients

When a patient discontinues from the study treatment (without reaching a protocol-defined endpoint), the Investigator will notify the principal Investigator as soon as possible (provided, in each case, patient care and safety are not compromised). When a patient discontinues the study treatment, a final visit will be conducted, preferably prior to the initiation of another anticancer therapy. However, these procedures should not interfere with the initiation of any new treatments or therapeutic modalities that the Investigator or patient's treating physician feel are necessary to treat the patient's condition. Following discontinuation of the study drug, the patient will be treated in accordance with the Investigator's/treating physician's best clinical judgment. At the final visit, the reason(s) for the discontinuation from the study will be recorded and a physical examination, body weight, vital signs measurement, laboratory analyses, performance status, tumor assessment, collection of unused study drug, and an assessment of adverse events will be performed as soon as possible after discontinuation from the study treatment. If a patient is discontinued from the study with an ongoing adverse event or an unresolved clinically significant laboratory result, the site will attempt to provide follow up until a satisfactory clinical resolution of the laboratory result or adverse event is achieved. In the event of a positive result on a pregnancy test for a patient during the study, the administration of study drug to that patient must be discontinued immediately.

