¹¹ End of Treatment visit should occur as soon as possible at the time of progression or discontinuation of treatment, preferably before the subject starts the next therapy, + 10 days from last dose. Imaging and tumor assessments do not need to be performed at this visit if performed within 30 days prior to the visit.

¹² Bone scan at investigator discretion

¹³ Long term follow up assessment (+/- 4 weeks). Patients will be contacted by phone call or e-mail for vital status data collection, adverse events evaluation (if AEs from study have not yet been closed), subsequent anti-breast cancer therapy (systemic therapy, radiation, or surgery), and development of a secondary malignancy.

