7.3. Assessment of Response by RECIST v1.1

RECIST v1.1 will be used by the Investigator as the primary measure for assessment of tumor response, date of disease progression, and as a basis for all protocol guidelines related to disease status.

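### PFS is censored at the close of follow-up although scheduled imaging ends at End of Treatment, so unscanned time counts as progression-free

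*Combined protocol and SAP*

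**What the plan says.** **Event.** Section 8.4.2.2, repeated in the synopsis, runs PFS from study entry to "first documented disease progression per RECIST v1.1 as assessed by local site or death". Section 7.3 makes RECIST v1.1 the "primary measure for assessment of tumor response, date of disease progression".

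**Censoring.** There is one rule: "Patients who are alive and free from progression on the date of closing follow-up will be censored on that date". Section 4.7 limits each patient's follow-up (death, loss to follow-up, withdrawal of consent, study discontinuation or 2 years). Section 4.1 schedules PFS analyses at 12 and 24 months without saying from when. Neither gives a study-level cut-off.

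**Imaging.** Scans are 8-weekly and may become 12-weekly after two consecutive scans showing CR, PR or SD (4.1, 4.3.9). At discontinuation, "tumor assessment, collection of unused study drug, and an assessment of adverse events will be performed as soon as possible" (4.3.12.1). Footnote 11 of Table 3 waives this in one case: "Imaging and tumor assessments do not need to be performed at this visit if performed within 30 days prior to the visit". The long-term follow-up column of Table 3 contains no imaging. A note in 7.5 adds "Every effort should be made to document the objective progression even after discontinuation of treatment", but sets no scans.

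**The other definition.** Section 7.6 also counts as disease progression "Clinical progression as determined by the Investigator, which may be characterized as, but is not limited to" two listed examples. For deaths it counts "Death from any cause that is not unequivocally unrelated to disease progression".

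**The concern.** Patients can leave treatment without RECIST progression by several routes: intolerance or unrelated illness (3.6.2.1), clinical progression or investigator decision (4.3.12), and symptomatic deterioration (7.5). After they stop, other anticancer therapy is allowed (3.4.2) and no scan is planned. Under the stated rule such a patient stays at risk and event-free from the last scan until death or the close of follow-up. Progression in that period would usually go unseen, so the Kaplan-Meier curve sits too high.

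This follows from the rule the plan states; it is not just a missing detail. In a single-arm trial no control group shares the bias. An unstated cut-off also leaves part of the PFS result to a choice made after the data are seen.

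**Working it through.** **Plan's own figures.** The plan gives no PFS event count or power to reproduce. Its only design figure is the Simon rule for ORR (2/30, then 8 or more of 50). It reproduces with exact type I error 0.0955 and power 0.8022, and does not involve PFS.

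**Inputs.**
- True median time to progression: 5 months (1.5, 12 earlier HR+/HER2- patients).
- Median survival after progression: 5 to 10 months, assumed. The same 12 patients had median PFS 5 and OS 10 months.
- Scan grids: every 8 weeks, or weeks 8 and 16 and then 12-weekly (the 8/16/12 grid).
- Share f leaving without RECIST progression: assumed at 10%, 20% and 30%. There are two loose anchors. In the first-in-human study 0 of 30 stopped for an adverse event (1.3); the exact 95% upper limit is 1 − 0.025^(1/30) = 11.6%. In the pancreatic trial 49 − 38 = 11 of 49 (22%) were not evaluable, with no reasons given (1.5).

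**Step 1: curve with no leavers.** One month is 365.25/(12 × 7) = 4.348 weeks. So λ = ln 2/(5 × 4.348) = 0.03188 per week, and 6 months is x = 26.09 weeks. With last scan g before x and post-progression death hazard μ = ln 2/(4.348m), where m is median survival after progression in months:

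S(6 months) = exp(−λg) − ∫ λ exp(−λt)[1 − exp(−μ(x − t))] dt, for t from g to x.

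- 8-week grid, g = 24: 0.4653 − 0.0010 = 46.4% (m = 5), or 0.4653 − 0.0005 = 46.5% (m = 10).
- 8/16/12 grid, g = 16: 0.6004 − 0.0251 = 57.5% (m = 5), or 0.6004 − 0.0133 = 58.7% (m = 10).

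**Step 2: the rule as written.** This was simulated with 400,000 patients per cell. Leaving hazard is f/(1 − f) × λ, independent of progression. There is an End of Treatment scan at stopping, 24-month uniform accrual, close at month 48, and follow-up for 24 months after stopping. Paired values are for m = 5 and m = 10.

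| Leavers | 8-week grid: 6-month PFS | Excess over Step 1 | 8/16/12 grid: 6-month PFS | Excess over Step 1 |
|---|---|---|---|---|
| 10% | 47.7, 48.2 | 1.3, 1.7 | 58.1, 59.3 | 0.6, 0.6 |
| 20% | 49.5, 50.1 | 3.1, 3.6 | 58.5, 60.0 | 1.0, 1.3 |
| 30% | 51.4, 52.3 | 5.0, 5.8 | 59.1, 60.8 | 1.6, 2.1 |

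Median on the 8-week grid: 5.5 months with no leavers and at 10%, 5.5 to 6.1 at 20%, 6.9 to 7.4 at 30%. On the 8/16/12 grid it is 6.4 months throughout.

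**Step 3: censoring at the last assessment, later deaths still events.** At 20% leavers, 6-month PFS is 48.7 and 48.4 on the 8-week grid, so the excess falls from 3.1 and 3.6 points to 48.7 − 46.4 = 2.3 and 48.4 − 46.5 = 1.9. On the 8/16/12 grid it is 58.0 and 58.9, leaving 0.5 and 0.2.

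**Step 4: clinical-only progressors.** Here leaving is itself progression. The chance of progressing in one 8-week interval is p = 1 − exp(−8 × 0.03188) = 0.225. If an assumed share f = 0.2 of progressions is clinical only and is censored, the event rate at each scan is (1 − f)p/(1 − fp) = 0.180/0.955 = 0.1885. Three scans give 0.8115³ = 53%. The rule as written gives 53 to 55%; counting clinical progression as an event gives 46%. Last-assessment censoring alone does not correct this group.

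**Step 5: sampling error.** At N = 50 the SD of 6-month PFS is about √(0.47 × 0.53/50) = 7 points (6.9 to 7.1 simulated). The 95% range of the estimated median is 3.7 to 9.2 months.

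**The case against.** **Which definition governs.** A reader might infer that the documents leave open whether 8.4.2.2 or 7.6 defines a PFS event. They do not support that. Section 8.4.2.2 names RECIST v1.1 in its own text, 7.3 points the same way, 7.5 classes deterioration without objective evidence separately, and 7.6 never mentions PFS. What stands is narrower: 7.6 differs on clinical progression and on unrelated deaths, and no sentence reconciles the two.

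**Close of follow-up.** Calling it wholly undefined would go too far, since 4.7 sets limits for each patient. Only the study-level cut-off is missing.

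**Follow-up content.** A reader of 4.5 and 4.7 might infer that later contact covers only survival and open adverse events. Section 4.3.13 and footnote 13 of Table 3 also list subsequent therapy, so the documents disagree. Neither version schedules imaging, so the point is unchanged.

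**Size.** The leaver share is assumed, and nothing in the documents anchors a share for clinical-only progressors. The End of Treatment scan will turn some of them into RECIST events. The plan reports the median, not 6-month PFS, and the median often does not move. Comparing the written rule with censoring leavers at their last scan would overstate the bias: that comparator itself falls as leavers rise (45.5% at 20% on the 8-week grid, against 46.4 to 46.5% with none), because End of Treatment scans find progression between scheduled scans. The table therefore uses the no-leaver curve. These objections limit the size; they do not remove the upward direction.

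**Conclusion.** The point holds as a modest, systematic upward bias in a secondary endpoint. The text is clear: the only censoring date is the close of follow-up, and scheduled imaging stops earlier.

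For leavers whose stopping is unrelated to progression, the excess in 6-month PFS is about 1 to 2, 3 to 4 and 5 to 6 points at 10%, 20% and 30% on the 8-week grid, and about 0.5, 1 and 2 points on the 8/16/12 grid. The median is unchanged at 10% and on the 8/16/12 grid; at 30% on the 8-week grid it rises by up to about 2 months (7.4 − 5.5 = 1.9). These figures rest on exponential progression with a 5-month median, the assumed shares, and a scan at every End of Treatment visit. The effect of clinical-only progressors has the same direction, but its size cannot be estimated from the documents.

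At modest shares the bias is below sampling error at N = 50. A reader might infer that the trial's conclusion is at risk. It is not: PFS is descriptive, and the ORR decision rule, sample size, alpha and power do not use it.

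**What to change.** 1. In 8.4.2.2 and the synopsis, censor patients without a PFS event at their last adequate tumour assessment, End of Treatment scan included, and state the data cut-off for each PFS analysis.
2. Add a cross-reference that 8.4.2.2 (RECIST v1.1 progression or any death) governs PFS and that 7.6 does not.
3. Add a sensitivity analysis that counts investigator-determined clinical progression as an event, because change 1 does not remove the bias from clinical progressors.
4. Optionally, add a sensitivity analysis for deaths after a long unscanned gap, since change 1 leaves part of the excess (Step 3). One version censors at the last assessment when death comes more than two scan intervals later. It should stay optional because it can overcorrect: at 20% leavers on the 8/16/12 grid it falls about 2 points below the no-leaver curve.

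The cost is wording in three places and one or two extra analyses, using scan, progression and death dates already collected. Reported PFS may look slightly shorter.

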8.4.2.3. Clinical Benefit rate at \geq 24 weeks

Clinical benefit rate (CBR) at \geq 24 weeks will be reported. The total number and percentage of patients who achieve complete response (CR), partial response (PR), or had stable disease (SD) at \geq 24 weeks will be reported.

8.4.2.4. Safety Assessments

Overall safety monitoring will be performed throughout the study. The safety of the SM-88 therapy will be assessed by evaluating study drug exposure, adverse events, serious adverse events, and all deaths.

A summarization of the number of days and/or cycles patients were exposed to study drug will be provided. Adverse events (and serious adverse events) will be graded and recorded throughout the study and during the follow-up period according to NCI CTCAE Version 5.0. Toxicities will be characterized in terms of seriousness, causality, toxicity grading, and action taken with regard to trial treatment. The percentage of patients experiencing an adverse event at a given severity, NCI CTCAE toxicity grade, and relationship to study drug will be provided. The number of patient deaths throughout the study will be summarized.

8.4.3. Exploratory Endpoints:

Descriptive statistics will be used to analyze any changes in cell-free DNA (cfDNA) measurement at baseline (pre-treatment on C1D1), during the SM-88 therapy, and at disease progression time points.

Baseline Characteristics

All baseline summary statistics and analyses will be based on characteristics prior to the initiation of study drug. Frequency and percentages for categorical variables, and mean (SD) or median (IQR, interquartile range) for the continuous variables based on the normalization of the data.

9. Correlative Research Management

9.1. cfDNA

Blood sample collection for analysis of cfDNA analysis will be collected at multiple time points: baseline (pre-treatment), C2D1, C3D1, at each additional restaging scan (every 8-12 weeks) and disease progression. cfDNA samples will be banked at Georgetown University, and eventually shipped to Foundation Medicine for analysis.

All specimens will be collected in two (2) 10 mL Streck cell-free DNA collection tubes (DNA BCT catalog # 230470). These vials shall be processed as per the laboratory instructions provided by Foundation Medicine, and categorized and banked at Georgetown as per protocol. Refer to the Lab Manual for more details on collection, processing, and storage instructions.

10. Ethical Considerations

10.1. Institutional Review Board (IRB)

GCP requires that the clinical protocol, any protocol amendments, the Investigator's Brochure, the informed consent and all other forms of patient information related to the study (e.g., advertisements used to recruit patients) and any other necessary documents be reviewed by an IRB. IRB approval of the protocol, informed consent and patient information and/or advertising, as relevant, will be obtained prior to the authorization of drug shipment to a study site. Any amendments to the protocol will require IRB approval prior to implementation of any changes made to the study design. Any serious adverse events that meet the reporting criteria, as dictated

by local regulations, will be reported to the IRB. During the conduct of the study, the Investigator should promptly provide written reports to the IRB of any changes that affect the conduct of the study and/or increase the risk to patients.

10.2. Ethical Conduct of the Study

The study will be conducted in accordance with the protocol, ICH guidelines, applicable regulations and guidelines governing clinical study conduct and the ethical principles that have their origin in the Declaration of Helsinki.

10.3. Patient Information and Consent

Prior to the initiation of any screening or study-specific procedures, the Investigator or his/her representative will explain the nature of the study to the patient and answer all questions regarding this study. Each informed consent will be reviewed, signed and dated by the patient and the person who administered the informed consent. A copy of each informed consent will be given to the patient and each original will be placed in the patient's medical record. An entry must also be made in the patient's dated source documents to confirm that informed consent was obtained prior to any study-related procedures and that the patient received a signed copy.

10.4. Ethical Consideration for Enrollment

Only patients with advanced cancer, for whom no curative therapy exists, will be considered for enrollment. The only treatment options for these patients are conventional chemotherapy, radiation, or participation in a clinical trial. As described above, the combination of SM-88 used with MPS is a rational and promising combination for such patients.

10.5. Protection of Patient Confidentiality

All patient records, questionnaires, and tissue specimens will be de-identified using a letter and number assigned to their case at the time of enrollment on study. No record or specimen will contain information which could identify the patient. The key which connects patient identifiable information with this assigned number will be held by the Principal Investigator. For computer records, the key will be protected by a double password protection system. Any paper records will be contained in a locked cabinet within a locked office to ensure patient's privacy is protected.

11.0 APPENDICES

APPENDIX A: STUDY ELIGIBILITY CHECKLIST

A Phase II trial of SM-88 in patients with metastatic hormone receptor-positive and HER2-negative (HR+/HER2-) breast cancer

Study ID: _____

Instructions: This form should be completed by the research staff before registering the patient into the trial.

Completed form can be emailed to Georgetown Project managers [REDACTED]

- MedStar Georgetown University Hospital
- MedStar Washington Hospital Center
- MedStar Franklin Square Medical Center
- MedStar Good Samaritan Hospital
- Hackensack University Medical Center

INCLUSION CRITERIA (ALL ITEMS MUST BE CHECKED YES)

YES NO	
 	Histologically or cytologically proven diagnosis of breast cancer with evidence of metastatic or locally advanced disease, not amenable to resection or radiation therapy with curative intent.
 	Documentation of ER-positive and/or PR-positive tumor ($\geq 1\%$ positive stained cells) based on most recent tumor biopsy (discuss with the Principle Investigator if results in different biopsies are discordant in terms of hormone receptor positivity) utilizing an assay consistent with local standards.
 	Documented HER2-negative tumor based on local testing on most recent tumor biopsy: HER2-negative tumor is determined as immunohistochemistry score 0/1+ or negative by in situ hybridization (FISH/CISH/SISH) defined by current ASCO/CAP (American Society of Clinical Oncology/College of American Pathologists) guidelines. Patients with equivocal HER2 in situ hybridization results according to current ASCO/CAP guidelines are eligible, as long as they have not received and are not scheduled to receive anti-HER2 treatment.
 	Must have progressed on (or been intolerant of) at least 2 lines of endocrine therapy in either the adjuvant or metastatic setting and progressed on (or been intolerant of) a CDK4/6 inhibitor.
 	Must have received no more than 4 lines of systemic therapy (for example, including but not limited to endocrine therapy, targeted therapy, biologic therapy, chemotherapy, or experimental therapy) for the treatment of breast cancer in the metastatic setting.
 	Life expectancy of more than 3 months.
 	Premenopausal or postmenopausal men or women.
 	Age ≥ 18 years
 	ECOG performance status (PS) of 0 to 1
 	Measurable disease by RECIST v1.1 criteria (tumor ≥ 1 cm in longest diameter on axial image on computed tomography (CT) or magnetic resonance imaging (MRI) or tumor ≥ 10 mm by caliper measurement on clinical exam and/or lymph node(s) ≥ 1.5 cm in short axis on CT or MRI) on baseline imaging. Lytic bone lesions or mixed lytic-blastic lesions with an associated soft tissue component ≥ 10 mm noted on CT or MRI are also included as per RECIST 1.1 criteria. Index lesions must not have undergone prior radiation therapy.
 	Asymptomatic brain metastases are allowed if the lesions are not considered to need local therapy. Previously treated brain metastases are allowed as long as they are > 4 weeks from local therapy, clinically asymptomatic, and not requiring high-dose corticosteroids. Patients may remain on steroids for CNS disease if they are taking a stable dose that is less than 10mg of prednisone per day, or the equivalent.
 	Must be capable of understanding and complying with parameters as outlined in the protocol and able to sign and date the informed consent, approved by the IRB, prior to the initiation of any screening or study-specific procedures.

 	
Pregnancy must be ruled out in women of childbearing potential. Serum or urine pregnancy test must be negative within 14 days of treatment start in women of childbearing potential and must be willing to have pregnancy test approximately every 4 weeks. Pregnancy testing does not need to be pursued in patients who are judged to be postmenopausal before enrollment, or who have undergone bilateral oophorectomy, total hysterectomy, or bilateral tubal ligation.
 
 ○ Patients may be considered postmenopausal in the case that one of the following criteria applies: 
 ▪ Prior bilateral oophorectomy, OR ▪ Age \geq 60 years, OR ▪ Age $<$ 60 years with intact uterus and amenorrheic for \geq 12 consecutive months prior to chemotherapy and/or endocrine therapy exposure, OR
 	
Willingness to utilize adequate contraception if of childbearing potential. Women of childbearing potential must use adequate contraception for the duration of protocol treatment and for at least 6 months after the last treatment with SM-88 used with MPS. Men must not donate sperm or conceive a child for the duration of protocol treatment and for at least 6 months after the last treatment with SM-88 used with MPS.
 
 ○ Adequate contraception is defined as one highly effective form (i.e. abstinence, (fe)male sterilization) OR two effective forms (IUD [non-hormonal preferred], condom with spermicidal foam / gel / film / cream / suppository, occlusive cap with spermicidal foam / gel / film / cream / suppository).
 	Must be able and willing to swallow pills whole and retain oral medication.
 	Resolution of all acute toxic effects of prior therapy, including radiotherapy to grade \leq 1 or patient's baseline (except toxicities not considered a safety risk for the patient) and recovery from surgical procedures.
 	Must have discontinued all previous therapies for cancer (including endocrine therapy, CDK4/6 inhibitor therapy, cytotoxic chemotherapy, targeted therapy [including, but not limited to, everolimus], radiotherapy, immunotherapy, and investigational therapy) for at least 14 days prior to receiving study drugs.

LAB VALUES (ALL MUST BE CHECKED YES)

YES NO	
 	ANC \geq 1,500/mm 3 ; Patients must be able to meet the criteria without receipt of colony stimulating factors within 2 weeks before obtaining sample
 	Platelets \geq 100,000/mm 3 ; Patients must be able to meet the criteria without transfusion within 2 weeks before obtaining sample
 	Hemoglobin \geq 9.0 g/dL; Patients must be able to meet the criteria without transfusion within 2 weeks before obtaining sample
 	Creatinine clearance \geq 55 mL/min based on Cockcroft-Gault equation
 	Hepatic function: AST and ALT \leq 3 \times the upper normal limit of institution's normal range. Total bilirubin \leq 1.5 \times the upper normal limit of institution's normal range (except for patients with a documented history of Gilbert's Syndrome who can be enrolled at PI discretion). For patients with liver metastases, AST and ALT \leq 5 \times the upper normal limit of institution's normal range, and total bilirubin $<$ 3.0 \times the upper normal limit of institution's normal range are acceptable as long as there is no persistent nausea, vomiting, right upper quadrant pain or tenderness, fever, or rash.
 	Alkaline phosphatase \leq 2.5 \times ULN (\leq 5.0 \times ULN if bone metastases present)

EXCLUSION CRITERIA (ELIGIBLE PATIENTS MUST ALL BE CHECKED NO)

YES NO	
 	Concurrent therapy with other approved or investigational cancer treatment agents, except bisphosphonates, RANKL inhibitors, GnRH agonists such as leuprolide or goserelin.
 	Inability to comply with study requirements.
 	Diagnosis of other invasive cancer except for adequately treated cervix cancer, or more than 5 years since other diagnosis of invasive cancer (including invasive squamous cell cancers due to contraindication for methoxsalen use) without current evidence of disease.
 	Impairment of gastrointestinal (GI) function or GI disease that may significantly alter the absorption of the study drugs (e.g., ulcerative diseases, uncontrolled nausea/vomiting, chronic diarrhea, malabsorption syndrome, intestinal obstruction, or small bowel resection) at discretion of investigator.
 	Patient with clinically significant liver disease, including active viral (including hepatitis B, hepatitis C, etc.) or other known hepatitis, current alcohol abuse, or cirrhosis.

 	Known chronic hepatitis B virus infection (testing not required prior to enrollment): 
 Patients with chronic Hepatitis C virus may be enrolled if there is no clinical/laboratory evidence of cirrhosis AND the patient's liver function tests fall within the parameters set in Section 3.2.
 	Uncontrolled HIV infection defined as any of the following 3 criteria: CD4 counts \leq 350 cells/ μ L; serum HIV viral load \geq 400 copies/mL; on a antiretroviral regimen for < 4 weeks prior to treatment with study drugs if anti-retroviral therapy is deemed necessary or appropriate by the Investigator.
 	Previous enrollment in this study or any other study investigating SM-88.
 	Clinically significant and uncontrolled major medical condition(s) including, but not limited to uncontrolled nausea/vomiting/diarrhea; active, uncontrolled infection; symptomatic congestive heart failure (New York Heart Association [NYHA] class \geq II); unstable angina pectoris; cardiac arrhythmia requiring hospitalization in the past 3 months; stroke or MI in the past 6 months.
 	Psychiatric illness or social situation that would limit compliance with study requirements.
 	Active uncontrolled or symptomatic brain metastases. Previously treated and clinically stable brain metastases, as per Investigator's judgement, are permitted.
 	Patients with a seizure disorder that is not well controlled or who have required a change in seizure medications within 60 days of enrollment to the trial
 	History of any known drug allergies to any study medication.
 	Patients with a history of hypersensitivity to phenytoin, its inactive ingredients, or other hydantoins; or a history of prior acute hepatotoxicity attributable to phenytoin.
 	Patients treated, or anticipated to be treated, with delavirdine (due to potential for loss of virologic response and possible resistance to delavirdine or to the class of non-nucleoside reverse transcriptase inhibitors caused by phenytoin).
 	Patients exhibiting idiosyncratic reactions to psoralen compounds.
 	Patients with a history of the light sensitive diseases for which methoxsalen would be contraindicated. Diseases associated with photosensitivity include lupus erythematosus, porphyria cutanea tarda, erythropoietic protoporphyrina, variegate porphyria, xeroderma pigmentosum, and albinism.
 	Patients with cutaneous melanoma or invasive squamous cell carcinomas or a history thereof, except for those in complete remission for \geq 5 years (due to contraindication for use of methoxsalen).
 	Patients with a hypersensitivity to sirolimus.
 	Patients with prior allogenic bone marrow transplant or solid organ transplant or being treated, or anticipated to be treated, with cyclosporine (because long-term administration of the combination of cyclosporine and sirolimus is associated with deterioration of renal function).
 	Patients treated, or anticipated to be treated, with a calcineurin inhibitor (because concomitant use of sirolimus and a calcineurin inhibitor increases the risk of calcineurin inhibitor-induced hemolytic uremic syndrome/thrombotic thrombocytopenic purpura/thrombotic microangiopathy [HUS/TTP/TMA]).
 	Women who are pregnant or breastfeeding.
 	Current use of known strong inhibitors or inducers of CYP3A4, CYP2C9 or CYP2C19 within 14 days of initiation of study drug. When possible these medications and grapefruit juice should be avoided for the duration of the study treatment and alternate therapies are preferred. For a list, refer to Section 3.5 or Appendix D of the protocol.

Study Coordinator Signature: _____ Date: _____

Investigator Signature: _____ Date: _____

Table 7: ECOG Performance Status Scale

Grade	ECOG
0	Fully Active, able to carry on all pre-disease performance without restriction.
1	Restricted in physically strenuous activity but ambulatory and able to carry out work of a light or sedentary nature, e.g., light housework, office work.
2	Ambulatory and capable of all self-care but unable to carry out any work activities. Up and about more than 50% of waking hours.
3	Capable of only limited self care, confined to bed or chair more than 50% of waking hours.
4	Completely disabled. Cannot carry on any self-care. Totally confined to bed or chair.

APPENDIX B: PATIENT REGISTRATION FORM**A Phase II trial of SM-88 in patients with metastatic hormone receptor-positive and HER2-negative (HR+/HER2-) breast cancer**

Study ID (IRB#): _____ Patient Initials: _____

Instructions: This form and all supporting documentation should be completed by the research staff and scanned/mailed to the Georgetown Project Managers ([REDACTED]) and Study PI ([REDACTED]).

Patient may not start treatment until eligibility is verified and Patient Study ID is assigned by Georgetown PMs.

Enrolling Site:

- MedStar Georgetown University Hospital (Lombardi Comprehensive Cancer Center)
- MedStar Washington Hospital Center
- MedStar Franklin Square Medical Center
- MedStar Good Samaritan Hospital
- Hackensack University Medical Center

1. Site PI: _____
2. Enrolling MD: _____
3. Date Informed Consent signed: ____ / ____ / ____
4. Date HIPAA Authorization signed: ____ / ____ / ____
5. Proposed Start Date for Treatment: ____ / ____ / ____
6. Treatment Location: _____
7. Date of Last Systemic anti-cancer therapy: ____ / ____ / ____
8. Prior Therapies (Date Initiated/Type):

9. Please fax documentation supporting eligibility per protocol (check those included):

- Eligibility Checklist
- Pathology Report
- Physicians Note
- Baseline CT/RECIST
- Laboratory Results (per protocol)
- Past Medical History
- ECOG score
- Other _____

